	
5. Subject has an indwelling catheter or practices intermittent self-catheterization.6. Subject has evidence of Urinary Tract Infection (UTI) Urine culture and sensitivity will be performed for positive leukocytes, or nitrites, or turbidity, or at the investigator's discretion, and will be confirmed with a culture greater than 100,000 cfu/mL If a subject has a UTI, at Screening (Visit 1) the subject can be rescreened after successful treatment of the UTI (confirmed by a laboratory result of negative urine culture).7. Subject has a chronic inflammatory condition such as interstitial cystitis, bladder stones, previous pelvic radiation therapy, or previous or current malignant disease of the pelvic organs (i.e., within the confines of the pelvis including the bladder and rectum in both sexes and the uterus, ovaries, and fallopian tubes in females; organs of the lower gastrointestinal tract are not necessarily considered pelvic organs as the distal ascending colon, the full transverse colon and proximal portion of the descending colon are in the abdomen).8. Subject resides in a nursing home.9. Subject is likely to enter a hospital or nursing home due to medical instability within the next 6 months in the opinion of the Investigator.10. Subject has received intravesical injection in the past 12 months with botulinum toxin, resiniferatoxin, or capsaicin.11. Subject has received electro-stimulation therapy for OAB (e.g., sacral nerve stimulation or PTNS).12. Subject began or has changed a bladder training program or pelvic floor exercises less than 30 days prior to Screening.13. Subject has moderate or severe hepatic impairment defined as Child-Pugh Class B or C.14. Subject has severe renal impairment defined as estimated creatinine clearance less than 29 mL/min determined by Estimated Glomerular Filtration Rate (eGFR, Cockroft-Gault, or MDRD formulae). A subject with end stage renal disease or undergoing dialysis is also not a candidate for the study.15. Subject has severe uncontrolled hypertension, which is defined as a sitting systolic blood pressure greater than or equal to 180 mmHg and/or diastolic blood pressure greater than or equal to 110 mmHg.16. Subject has evidence of QT prolongation on ECG defined as QTc greater than 450 msec for males, QTc greater than 470 msec for females or a known history of QT prolongation.17. Subject has a clinically significant ECG abnormality, as determined by the Investigator.18. Subject has AST or ALT greater than 2x upper limit of normal (ULN), or γ-GT greater than 3x ULN and considered clinically significant by the Investigator.

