1.2.2 Summary of the Pharmacokinetics of Mirabegron

After oral administration of mirabegron in healthy volunteers, peak mirabegron plasma concentrations were attained between 3 to 5 hours. The absolute bioavailability increases from 29% at a dose of mirabegron 25 mg to 45% at a dose of mirabegron 150 mg under fasted conditions in healthy volunteers. Mean C_{max} and AUC_{inf} increased more than dose proportionality over the recommended dose range. Steady state concentrations were achieved within 7 days of once daily dosing with mirabegron. The C_{max} and AUC_{tau} of

mirabegron and its metabolites following multiple oral doses in older adult subjects (≥ 65 years) were similar to those in younger subjects (18 to 45 years). The C_{max} and AUC_{tau} of mirabegron were approximately 40 – 60% higher in females than in males. The mean terminal $t_{1/2}$ is comparable in both sexes. Evaluation of special populations in the phase 1 studies demonstrated that volunteers with severe renal impairment (CRCL 15 to 29 mL/min or eGFR 15 to 29 mL/min per $1.73m^2$) or moderate hepatic impairment (Child-Pugh Class B) had an approximately 2-fold increase in exposure to mirabegron relative to normal healthy volunteers.

The in vitro oxidative metabolism of mirabegron in human liver microsomes is primarily mediated by cytochrome P450 (CYP) 3A4, but a possible role for CYP2D6 could not be excluded. In vitro CYP inhibition studies suggest that mirabegron is a moderate and time-dependent inhibitor of CYP2D6 and a weak inhibitor of CYP3A4.

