13. Subject has moderate or severe hepatic impairment defined as Child-Pugh Class B or C.
14. Subject has severe renal impairment defined as estimated creatinine clearance less than 29 mL/min determined by Estimated Glomerular Filtration Rate (eGFR, Cockcroft-Gault, or MDRD formulae). A subject with end stage renal disease or undergoing dialysis is also not a candidate for the study.

15. Subject has severe uncontrolled hypertension, which is defined as a sitting systolic blood pressure greater than or equal to 180 mmHg and/or diastolic blood pressure greater than or equal to 110 mmHg.
16. Subject has evidence of QT prolongation on ECG defined as QTc greater than 450 msec for males, QTc greater than 470 msec for females or a known history of QT prolongation.
17. Subject has a clinically significant ECG abnormality, as determined by the Investigator.
18. Subject has AST or ALT greater than 2x upper limit of normal (ULN), or γ -GT greater than 3x ULN and considered clinically significant by the Investigator.
19. Subject has a hypersensitivity to any components of mirabegron, other β -AR agonists, or any of the inactive ingredients.
20. Subject has any clinically significant condition, which in the opinion of the Investigator makes the subject unsuitable for study participation.
21. Subject has been treated with an experimental device within 28 days or received an investigational agent within 28 days or 5 half-lives, whichever is longer, prior to Screening.
22. Subject has a concurrent malignancy or history of any malignancy (within the past 5 years), except non-metastatic basal or squamous cell carcinoma of the skin that has been treated successfully.
23. Subjects with current history of alcohol and/or drug abuse.
24. Subject is using prohibited medications which cannot be stopped safely during the period defined in Appendix 1.
25. Subject has stopped, started or changed the dose of a restricted medication (defined in Appendix 1) within the last 30 days prior to Screening.
26. Subject is involved in the conduct of the study as an employee of the Astellas group, third party associated with the study, or the study site team.
27. Subject has previously received mirabegron.

Exclusion Criteria assessed after placebo run-in period at Visit 3 (Baseline):

1. Subject fulfills any exclusion criteria of Visit 1 (subject does not need to repeat screening assessments [PVR, cough provocation test, chemistry/hematology/urinalysis]).

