2. Subject was non-compliant during 2-week placebo run-in period, defined as taking less than 80% and greater than 120% of study medication.
3. Subject has any systolic blood pressure measurement \geq 180 mmHg or diastolic blood pressure measurement \geq 110 in the 3-day diary or during the baseline visit.

Waivers to the exclusion criteria will NOT be allowed.

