5 TREATMENTS AND EVALUATION

5.1 Dosing and Administration of Study Drugs and Other Medications

5.1.1 Dose/Dose Regimen and Administration Period

Subjects will be randomized to one of two treatment groups in a 1:1 ratio to either mirabegron or placebo (PBO). Randomization will be stratified by age < 75 years and ≥ 75 years. Those subjects randomized to mirabegron will start at 25 mg and may increase to 50 mg after 4 weeks or 8 weeks based on individual subject efficacy, tolerability and Investigator discretion. Those subjects randomized to PBO will start blinded product matched to the mirabegron 25 mg tablet and may also increase to 50 mg PBO after 4 or 8 weeks. Once a patient has increased dose, they will remain on that dose for the remainder of the study unless for safety reasons that require discontinuation of study drug.

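### Exclusion 14 excludes estimated clearance below 29 mL/min, one unit short of the 15 to 29 range that Protocol section 1.2.2 calls severe, so a subject at 29 is not excluded by it

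*Protocol*

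**What the plan says.** Criterion 14 appears in the Protocol synopsis and in section 3.3 with the same cut-off: "Subject has severe renal impairment defined as estimated creatinine clearance less than 29 mL/min", determined by eGFR, with Cockcroft-Gault and MDRD also accepted. End-stage renal disease and dialysis are excluded separately in the same item. Section 3.3 closes with "Waivers to the exclusion criteria will NOT be allowed".

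The pharmacokinetic summary in Protocol section 1.2.2 uses the same label, severe renal impairment, for a slightly wider range. It refers to phase 1 "volunteers with severe renal impairment (CRCL 15 to 29 mL/min or eGFR 15 to 29 mL/min per" 1.73 m²). These volunteers, and those with moderate hepatic impairment (Child-Pugh B), "had an approximately 2-fold increase in exposure to mirabegron relative to normal healthy volunteers".

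Criterion 13 deals with the hepatic group: "Subject has moderate or severe hepatic impairment defined as Child-Pugh Class B or C".

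On dosing, Protocol section 5.1.1 starts subjects on mirabegron at 25 mg, and they "may increase to 50 mg after 4 weeks or 8 weeks based on individual subject efficacy, tolerability and Investigator discretion". It sets no renal condition on the increase. Section 1.3.1 states that the QT, heart-rate and blood-pressure risks grow as exposure grows.

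**The concern.** The criterion is meant to keep severe renal impairment out of the trial, but its strict inequality leaves out the top value of the range that the protocol itself calls severe. The protocol gives no reason for this. Amendment 2 revised this criterion, and its stated reason is only that sites do not need a 24-hour urine collection.

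The other group with about doubled exposure, Child-Pugh B, is excluded in full by criterion 13. This suggests, but does not prove, that the renal group was also meant to be excluded in full.

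At stake is a subject-safety boundary. A subject at 29 could enter and be raised to 50 mg, although the protocol places that subject in a higher-exposure group and says that certain cardiovascular risks rise with exposure. Because waivers are barred, the written number carries weight.

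**Working it through.** The plan gives no figure to reproduce here, so the check compares two ranges. Let x be the estimated clearance.

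**Inputs**

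- Excluded by criterion 14 (synopsis and section 3.3): x < 29.
- Severe group in section 1.2.2: 15 ≤ x ≤ 29.

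**Severe by section 1.2.2 but not excluded by criterion 14**

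1. Whole-number results. The range 15 to 29 holds 29 − 15 + 1 = 15 values. Criterion 14 covers 15 to 28, which is 28 − 15 + 1 = 14 values. The one left over is x = 29.
2. Decimal results, with 15 to 29 read literally as end points. Only x = 29.0 is left over.
3. Decimal results, with 15 to 29 taken as whole-number categories. The values 29.0 to 29.9 are left over.

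The documents do not say how results are reported, so all three readings stay open. The gap is at most one unit.

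**What happens to such a subject**

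1. Not being excluded by criterion 14 is not the same as being eligible. Every other criterion still applies, including criterion 20, which lets the investigator exclude for any clinically significant condition.
2. If the subject does enter, section 5.1.1 permits 50 mg at Week 4 or Week 8 with no renal limit.
3. Table 3 of the Protocol schedules creatinine only at Screening and Week 12, and section 3.3 says that chemistry need not be repeated at Visit 3. The screening value is therefore the only scheduled renal check before a dose increase.

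**Which replacement closes the gap**

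| Cut-off | Whole numbers | Decimals, literal range | Decimals, whole-number categories |
|---|---|---|---|
| below 29 (present) | 29 left over | 29.0 left over | 29.0 to 29.9 left over |
| 29 or below | none | none | 29.1 to 29.9 left over |
| below 30 | none | none | none |

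Only below 30 works under all three readings.

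**The case against.** The strongest reply is that nothing conflicts in operation. The synopsis and section 3.3 agree, section 1.2.2 is background that no site applies, and an entry threshold need not copy the range of a phase 1 cohort. This is right as far as it goes: sites have one rule. A reader might infer that sites receive contradictory instructions; they do not. What remains is that the rule names a group and stops short of the protocol's own description of that group, without explanation.

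Second, one unit is finer than the criterion can resolve. Clearance is estimated, three formulae are accepted, and section 1.2.2 uses mL/min for creatinine clearance but mL/min per 1.73 m² for eGFR. Classification near the boundary can depend on the formula. This stands, and it is a reason to state the units in the fix, but it does not justify the present number.

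Third, the harm is already contained. ECG and vital signs are taken at every in-office visit. Criteria 15 to 17 exclude severe uncontrolled hypertension, QT prolongation and clinically significant ECG abnormalities. Titration depends on tolerability and the investigator's judgement, and a subject can be discontinued in his or her own interest. Section 1.2.2 also reports exposure 40 to 60% higher in females than in males, and the protocol titrates both sexes without a cap. All of this limits the size of the point.

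Finally, a reader might infer that 50 mg at a clearance of 29 acts like about 100 mg in a subject with normal renal function. The documents do not support that. The roughly doubled exposure describes a group spanning 15 to 29, and nothing is given for its mildest edge. Nor does exposure convert directly to dose: "The absolute bioavailability increases from 29% at a dose of mirabegron 25 mg to 45% at a dose of mirabegron 150 mg", and section 1.2.2 says that exposure rises more than in proportion to dose.

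**Conclusion.** The point holds as a very small safety correction to an entry threshold. A subject at 29, or at 29.0 to 29.9 on the widest reading, falls in the protocol's severe group, is not excluded by criterion 14 and, if otherwise eligible, may reach 50 mg.

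The width of the gap rests on how clearance results are reported, which the documents do not state. The number of subjects affected is not given either; very few are expected with a gap of one unit. Exposure at 29 is unknown, so no dose equivalent or excess risk can be attached. Section 1.2.3 says that doses of 25 to 200 mg daily have been studied in patients with overactive bladder, which is a further reason not to read this as a serious hazard. Power, type I error and the efficacy analysis are not affected. Whether the cut-off was a drafting slip or a choice cannot be settled from the documents.

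**What to change.** In criterion 14, in both the synopsis and section 3.3, lower-bound eligibility at 30: exclude estimated clearance less than 30 mL/min, or less than 30 mL/min per 1.73 m² when the result is an eGFR or MDRD value.

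The cost is an amendment to wording in two places. A very few borderline subjects become ineligible; the sample size and the analysis do not change.

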--	--

	
Analysis on Secondary Endpoints The change from baseline to end of treatment for other secondary endpoints (excluding mean voided volume [MVV]) will be analyzed using a similar ANCOVA model as described above for mean number of micturitions per 24 hours. The change from baseline to end of treatment in MVV will be analyzed using the Stratified Rank ANCOVA and ANCOVA model as described above for mean number of incontinence episodes.
 
Safety: Safety analyses will be performed on the Safety Analysis Set (SAF) defined as all subjects who receive at least one dose of double-blind medication. Number and percentage of treatment-emergent adverse events reported during the double-blind period will be summarized by system organ class, preferred term, seriousness, severity, and relationship to treatment, overall and by treatment group.
 
Statistical differences in change from baseline to end of treatment in cognitive assessment will be tested using a paired sample Wilcoxon test.
 
Changes from baseline for PVR and laboratory assessments (biochemistry and hematology) will be summarized in tables by treatment group and visit.
 
Vital sign data will be analyzed separately based on the 3-day diary and the site assessment at each clinic visit. Change from baseline in vital sign variables will be analyzed using the same ANCOVA model as described for the analysis of change from baseline in mean number of micturitions per 24 hours. No p-values will be calculated.
 
ECGs will be performed at Screening (Visit 1), the placebo run-in period (Visit 2), Baseline (Visit 3), Week 4 (Visit 4), Week 8 (Visit 5), and Week 12/End of Treatment (Visit 6).
 
Interim Analysis: N/A

--	--

V. FLOW CHART AND SCHEDULE OF ASSESSMENTS

Figure 1 Flow Chart

[figure not shown]

Table 1 Schedule of Assessments

	Screening	Placebo Run-In	Treatment Period				Follow-up Phone Call
			1	2	3	4	
Visit	1	2	3	4	5	6	7
Day	-28	-14	1	28	56	84	112
Week	-4	-2	0/Baseline	4	8	12/EOT	16
Visit Windows (Days) ^a	+/- 10	+/- 3	+/- 3	+/- 7	+/- 7	+/- 7	+/- 3
Informed Consent/HIPAA	X						
Inclusion/Exclusion Criteria	X		X				
Medical History and OAB History	X						
Demographics	X						
Enter 2-week Placebo Run-in ^b		X					
Randomization ^c			X				
Physical Exam (including height ^d and weight)	X						X
Vital Signs – in office (includes pulse and blood pressure)	X	X	X	X	X	X	
Cough Provocation test (Females only)	X						
Serum chemistry, hematology & urinalysis ^e	X						X

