1 INTRODUCTION

1.1 Background

Overactive bladder (OAB) is a frequent condition affecting older adults. It is estimated that more than half the elderly population experience voiding dysfunction, which may be attributed to idiopathic, neurologic, or cognitive impairment [Nassau et al, 2014]. The frequency and urgency associated with OAB are often highly debilitating. In addition, OAB-related urinary incontinence (UII, MUI) has been associated with other deleterious health related outcomes in community dwelling seniors, including falls and fractures, urinary tract infections, skin infections, depression, and chronic constipation [Wagg et al, 2014; Wagg et al, 2013; Kashyup et al, 2014]. Antimuscarinic anticholinergics in immediate-release and sustained-release formulations have been demonstrated to be efficacious in controlling urgency and incontinence episodes in older adults. However, their anticholinergic properties have been shown in several studies to be especially concerning for the older adult patients. As a result of the combination of age-related changes in blood-brain barrier permeability and comorbidity-related changes in cerebrovascular status, impaired cognitive function has been associated with increasing anticholinergic drug burden [Boustani et al, 2008; Cai et al, 2013; Fox et al, 2011].

Older patients are known to experience more AEs than younger patients and the AEs they experience with oral antimuscarinic treatment may be more pronounced [Wagg et al, 2010; Allman et al, 2006]. Of particular concern are the potentially adverse effects of antimuscarinic medications caused by age-related changes in central cholinergic transmitter systems [Kay et al, 2005]. Indeed, immediate and extended-release formulations of oxybutynin have been associated with cognitive impairment in older people who are cognitively intact although trospium chloride, as well as other newer antimuscarinics, have been reported to have no adverse effects on cognition in the cognitively-intact older adult patients and those with mild cognitive impairment [Wagg et al, 2013; Boustani et al, 2008; Cai et al, 2013; Fox et al, 2011; American Geriatrics Society, 2012; Kay et al, 2006; Holick 2008].

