There is evidence that vitamin D plays a role in the pathophysiology of OAB. Calcium is involved in bladder function through its role in detrusor smooth muscle contraction. In a study of women with OAB, a deficiency in dietary vitamin D was found to lead to a higher incidence of OAB symptoms [Dallosso et al, 2004]. Another study found that treatment of women with a vitamin D analog improved symptoms of OAB [Digesu et al, 2012]. Although the elderly are at high risk of having vitamin D deficiency, there are currently no data evaluating the vitamin D status of patients with OAB related to efficacy on OAB oral therapy [Holick 2008].

In conclusion, this will be the first mirabegron OAB study to specifically evaluate the efficacy and safety of mirabegron in an older population of patients with OAB. This study will also be the first to explore the effect of mirabegron on cognitive function in older adult patients. Oral antimuscarinic agents have historically been the preferred treatment option for OAB; however, these agents can be suboptimal in their effect and lead to burdensome adverse events, as seen in previous studies in older patients. This study is designed to demonstrate the reduction in frequency of incontinence episodes and micturitions in older adults (> 65 years) and support that mirabegron is a suitable option for the treatment of OAB in older patients with multiple comorbidities, not adversely affecting cognitive function in patients with impaired mental status, and increasing quality of life.

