7.4.4 Exploratory Analysis

7.5 Analysis of Safety

Safety analysis will be performed for adverse events (AEs) and vital signs using the SAF. No inferential comparison between treatment groups will be performed for the safety analysis in

this study with the exception of the change from baseline in Montreal Cognitive Assessment Test (MoCA) and for vital signs analysis.

Differences in change from baseline of MoCA scores between mirabegron and placebo will be analyzed using a stratified ANCOVA model. The response variable will be the change from baseline in MoCA scores. Treatment group and gender will be fixed factors in the model while the baseline symptom bother and total health related quality of life scores will be included as covariate. Age group (<75, \geq 75) will be included as the stratification factor. As part of the ANCOVA results, LS means and two-sided 95% CIs for mean changes from baseline within each treatment group will be provided.

Vital Signs will be summarized by treatment group and by Home Based Blood Pressure Monitoring (HBPM) versus office based using descriptive statistics for baseline value, specified post-baseline time point values (Week 4, Week 8, Week 12/EOT), and change from baseline to each specified post-baseline time points. Office based and morning and evening blood pressure will be reported separately. For HBPM the first reading from each time period will be discarded and the subsequent two readings for each time period will be averaged over the 3-day diary. HBPM and office based monitoring will be reported separately (See [Appendix 4](#)).

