7.5.4 Montreal Cognitive Assessment Test (MoCA)

The observed values and change from baseline values for MoCA total points and its subscale items (Attention, Language, Naming Visuospatial/Executive, Abstraction Points, Delayed Recall Points, and Orientation Points) by treatment group will be presented in a by-patient listing and in a summary table.

Differences in change from baseline of MoCA scores between Mirabegron and placebo will be analyzed using a stratified rank ANCOVA model. The response variable will be the change from baseline in MoCA scores. Treatment group and gender will be fixed factors in the model.. A subset analysis by age group (<75 , ≥ 75) will be included.. As part of the ANCOVA results, LS means, two-sided 95% CIs, and p-values for mean changes from baseline within each treatment group will be provided.

A simpler model will also be provided that includes only treatment, gender, and baseline MoCA values as covariates.

A shift table for MoCA total points by treatment group will be created by the following categories:

- >26: normal
- ≤ 26 : impaired
 - 18-26: mild cognitive impairment
 - 10-17: moderate cognitive impairment
 - <10: severe cognitive impairment.

The following MoCA data will be presented graphically by treatment group across visits:

- MoCA results using mean (+/- 95% CI) plot,
- Change from baseline in MoCA results using mean (+/- 95% CI) plot.

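### MoCA, the trial's only cognitive measure, has three inconsistent planned analyses: one makes no comparison with placebo, and neither main between-arm model names baseline MoCA as a covariate

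*Protocol*

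**What the plan says.** MoCA is given at Baseline and at Week 12/End of Treatment (protocol section 5.4.3). SAP section 7.5 makes it the one exception to the rule against inferential comparison of arms on safety data. Its analysis is described in three places.

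- **Protocol synopsis, Statistical Methods, Safety:** "Statistical differences in change from baseline to end of treatment in cognitive assessment will be tested using a paired sample Wilcoxon test". No treatment contrast is mentioned.
- **Protocol section 7.5:** "Differences in change from baseline of MoCA scores between mirabegron and placebo will be analyzed using a stratified ANCOVA model". Treatment and gender are factors and age group is the stratification factor, but "the baseline symptom bother and total health related quality of life scores will be included as covariate". Baseline MoCA is not named. The listed output is LS means and CIs for change within each arm.
- **SAP section 7.5.4:** "Differences in change from baseline of MoCA scores between Mirabegron and placebo will be analyzed using a stratified rank ANCOVA model". The named terms are treatment and gender, and age group appears as a subset analysis. The listed output is LS means, CIs and p-values for change within each arm. It then says: "A simpler model will also be provided that includes only treatment, gender, and baseline MoCA values as covariates".

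The generic rank ANCOVA code in SAP section 7.1.2 does regress the change rank on the baseline rank and gender within age group. It ends in a CMH test of the residuals by treatment.

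**The concern.** Both objectives are stated as mirabegron versus placebo, and the protocol's Background presents this as the first study to explore mirabegron's effect on cognition. A reader of the results will want the difference between arms in MoCA change, with its uncertainty. None of the three MoCA descriptions lists that quantity among its outputs.

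The synopsis test is the most serious of the three. A paired test asks whether scores moved between two visits. Any shift that has nothing to do with the drug, such as familiarity with the test at the second sitting, counts as signal. An inert drug could then appear to improve cognition, and a real decline offset by practice could go unseen.

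The covariate problem is milder. Baseline OAB-q scores measure bladder symptoms and their burden, and nothing in the documents links them to change in MoCA. Protocol section 7.4.2 uses the same covariate wording for PPBC, which suggests copied text. SAP section 7.4.3 corrected the PPBC model to use the baseline scores. SAP section 7.5.4 removed the OAB-q covariates from the MoCA model but put nothing in their place. SAP section 7.5.3 flags its departure from the protocol for vital signs; section 7.5.4 gives no such note.

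**Working it through.** The documents give no SD, power, margin or sample size for MoCA, so there is no planned figure to reproduce. The size of each problem has to be shown under assumptions.

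**Inputs.** From the documents: 340 evaluable subjects per arm (protocol section 7.1), 1:1 allocation, two-sided 0.05. Assumed: SD of MoCA change 2 to 3 points; a practice gain of 0.5 points in both arms; no drug effect; baseline/Week 12 correlation r from 0.5 to 0.8; equal variance at the two visits.

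**1. Paired test within one arm, no drug effect** (normal approximation). z = 0.5 / (SD/√340), with √340 = 18.44; probability of significance = Φ(z − 1.96).

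| SD of change | z | Probability of p < 0.05 |
|---|---|---|
| 2.0 | 4.61 | 99.6% |
| 2.5 | 3.69 | 95.8% |
| 3.0 | 3.07 | 86.7% |

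A simulation of the Wilcoxon test itself (2,000 trials per setting, scores rounded and limited to 0–30, MoCA SD 3, mean 24, r = 0.5, 0.7, 0.85) gave 85 to 100% for a 0.5-point gain, 43 to 90% for 0.3 points, and about 5% with no gain.

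**2. Between-arm comparison of change, same conditions.** A shift common to both arms drops out of the difference. In the same simulation, over practice gains of 0 to 1.0 point, the error rate was 3.8 to 5.5% without baseline MoCA and 4.1 to 5.2% with it.

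**3. A real decline offset by practice.** If the drug lowers MoCA by 0.5 and practice raises it by 0.5, the mean change on mirabegron is 0 and the paired test has nothing to detect. The between-arm test has SE = SD × √(2/340) = SD × 0.0767, and power = Φ(0.5/SE − 1.96):

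- SD 2.0: SE 0.153, power 90.3%
- SD 2.5: SE 0.192, power 74.1%
- SD 3.0: SE 0.230, power 58.4%

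Setting the decline equal to the practice gain is the extreme case; it shows the mechanism.

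**4. What leaving out baseline MoCA costs.** The variance of the arm difference is proportional to 2(1 − r) for an unadjusted change score and to 1 − r² with baseline adjustment. The reduction is 1 − (1 − r²)/[2(1 − r)] = (1 − r)/2.

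| r | Variance reduction |
|---|---|
| 0.5 | 25% |
| 0.6 | 20% |
| 0.7 | 15% |
| 0.8 | 10% |

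On the CI width this is √0.75 = 0.87 to √0.90 = 0.95 of the unadjusted width. The simulated reduction, with r up to 0.85, was 8 to 27%.

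**The case against.** The paired test appears only in the synopsis. Protocol section 7 leaves the details of analysis to the SAP, and SAP section 7.5.4 contains no paired test, so the 87 to 99.6% figure describes a test that may never be run. The SAP may also handle baseline already. The rank code in section 7.1.2 carries the baseline rank and stratifies by age group. The general ANCOVA text there includes the baseline value and promises a difference in LS means with a CI. Calling the second MoCA model simpler suggests that the main one holds at least the same terms.

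Much of this stands. If the section 7.1.2 code is what runs, most of the precision in step 4 is already captured. But section 7.5.4 does not refer to that code, lists its own shorter set of terms, and does not say which model is the main one. The rank code gives a CMH p-value with no effect estimate. No rule says that the synopsis gives way.

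Three stronger readings are tempting, and the documents do not support them.

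- **That practice or recovery after stopping earlier drugs cannot be told from a drug effect in any of the MoCA analyses.** This is true of the paired test and of the within-arm p-values, but not of the two between-arm models, where randomisation makes common drift cancel (step 2).
- **That drug washout is a major source of drift.** The Background says "impaired cognitive function has been associated with increasing anticholinergic drug burden", but nothing about recovery time after stopping. Prohibited drugs stop at least 30 days before Screening, and Baseline is at least 18 days after that (Table 1, footnote a). So at least 30 + 18 = 48 days pass before the first MoCA, and any remaining recovery is expected equally in both arms.
- **That the trial owes a between-arm estimate in cognitively impaired subjects.** The phrase "not adversely affecting cognitive function in patients with impaired mental status" is in the Background. The objectives and endpoints make no such claim, and the SAP already plans a shift table over MoCA categories by arm.

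**Conclusion.** The point holds as an inconsistency among three analyses, with two separate consequences. The synopsis test does not answer the mirabegron-versus-placebo question. Under the assumptions above it would be significant within an arm in about 87 to 99.6% of trials with an inert drug. Those percentages apply to that test alone and rest on an assumed practice gain and SD. The between-arm models in protocol 7.5 and SAP 7.5.4 are valid comparisons. Leaving out baseline MoCA does not bias them; it forgoes a variance reduction of about 10 to 25% relative to an unadjusted change score, and adjustment for chance imbalance at baseline. That range is for the SAP wording read literally. It applies to the protocol model only so far as OAB-q baselines explain little of MoCA change. Whatever the assumptions, the main MoCA model is not clearly identified and the MoCA text does not list the between-arm difference with a CI.

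**What to change.** 1. **Protocol synopsis:** delete the paired Wilcoxon sentence and refer to section 7.5.
2. **Protocol section 7.5:** replace the baseline OAB-q covariates with baseline MoCA.
3. **SAP section 7.5.4:** name one main analysis, the mirabegron-minus-placebo difference in MoCA change with its 95% CI, adjusted for baseline MoCA, gender and age group. Keep the stratified rank ANCOVA as support, and state that it includes the baseline rank. Within-arm estimates can stay as description, without p-values.

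The cost is wording in three places and a revised table layout, with no new data.

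An estimate by baseline MoCA category is optional. It would first need the cut-off settled: SAP section 7.5.4 counts a score of 26 as impaired, while the form in SAP Appendix 5 counts 26 as normal.
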